THE OVERALL HYPOTHESIS TO BE TESTED IN THIS TRIAL is that the early introduction of combination therapy of corticosteroids and either MTX or CsA will prove more effective and safe than corticosteroids alone in the treatment of JDM.

Trial Design and Duration. Two-year single-blind (assessor blinded to treatment arm of subject), randomised, actively controlled, multi-centre, international prospective, superiority trial of different combination of drugs. Patients will be then followed for up to 5 years for the evaluation of long term morbidity and mortality.

Dose Regimen (see figure 1):

3 daily pulses of intravenous (iv) methylprednisolone (30 mg/kg/pulse max 1 g/pulse) followed by randomisation into one of these 3 groups.

Induction of remission

Group 1 prednisone or equivalent (PDN): PDN 2 mg/kg/day (see below for rules regarding PDN administration);

Group 2 PDN+cyclosporine A (CsA): PDN 2 mg/kg/day + CsA 5 mg/kg/day in 2 oral doses.;

Group 3 PDN + methotrexate (MTX): PDN 2 mg/kg/day + MTX 15-20 mg/m² once per week. Patients treated with MTX will receive concomitant folic or folinic acid according to the attending physician decision.

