Suggested MTX administration: MTX will be administered parenterally (subcutaneously, intramuscularly) at 15-20 mg/m² once per week. In case of MTX related toxicity (eg transaminase increase) stop MTX for 2 weeks and if adverse event disappear start again at 10 mg/m² once per week and increase of 2.5 mg/m² once per week every week until the maximum tolerated dose (max 20 mg/m² once per week). If adverse event persist stop methotrexate. Patients treated with MTX will receive concomitant folic (1 mg/day except the day of MTX administration) or folinic acid (25-50% of the MTX dose in mg; to be administered the day after MTX administration) according to the attending physician decision.

Long term follow up after month 24 until month 60. All patients will be followed for a total of 5 years for the assessment of long term morbidity and mortality rate. After month 24 treatment will be left open to the physician decision based on the clinical status of the patient.

Important: Medications will be supplied by the pharmacy of the participating centre and covered with the standard way of reimbursement in each participating country.

Subject Population. Newly diagnosed and untreated children with probable or definite diagnosis of JDM according to Bohan and Peter Criteria (12;13).

Figure 1: JDM study design

Efficacy Parameters:

Primary Outcome Measures after 6 months of treatment. According to the PRINTO definition of improvement for JDM, patients will be considered responders to therapy if they will demonstrate at least 20% improvement in at least 3 core set variables with no more than 1 of the remaining variables, (muscle strength excluded), worsened by > 30% (4).

The PRINTO JDM core set variables (4) are:

- 1) muscle strength by the mean of the Childhood Myositis Assessment Scale (CMAS);
- 2) physician's global assessment of disease activity on a 10 cm VAS ;
- 3) global disease activity assessment by the mean of the Disease Activity Index (DAS);
- 4) parent's/patient's global assessment of overall well-being on a 10 cm VAS;
- 5) functional ability assessment by the mean of the Childhood Health Assessment Questionnaire (CHAQ)
- 6) health-related quality of life assessment.

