Primary Outcome Measures after 24 months of treatment: a) time to clinical remission on medication defined as normal muscle strength and physician global assessment of disease activity equal to 0; b) time to flare of the disease defined as at least 20%, worsening from the previous evaluation value in 2 of any 6 JDM core set measures with no more than 1 of the remaining improved by more than 30% (muscle strength excluded).

Effectiveness: the rate of retention on treatment will be used as main measure of effectiveness.

Secondary Outcome Measures. Change over time in the individual components of the JDM core set of variables; time to muscle enzymes normalisation; frequency of drop-out of suggested steroids use; frequency of drop-out for inefficacy of treatment.

Safety Parameters.

- 1) Incidence of adverse events (AE):
 - a) Number of patients discontinuing trial due to on-therapy conditions and AE possibly, probably, or definitely related to the experimental therapy, and listing of AE that cause discontinuation.
 - b) Number of patients for whom the dosage was lowered, or withheld temporarily, due to AE, and listing of the specific AE that caused such action.
 - c) Complete list of AE by system.
- 2) Incidence of clinically significant changes in laboratory parameters.
- 3) Drop out rate due to toxicity.

Inclusion Criteria. Each patient must meet all the following criteria in order to participate in this trial:

- 1) Newly diagnosed and untreated children (only treatment with 1 NSAID is allowed and/or prednisone >1 mg/kg/day for no more than 1 month from diagnosis) with probable or definite diagnosis of JDM according to the Bohan and Peter criteria (12;13). If a muscle biopsy will be performed (optional) it will be read by the pathologists of the participating centres (light and immunofluorescence). Slides of paraffin-embedded sections from all patients will be re-viewed by a blinded myopathologist at PRINTO.
- 2) Age at enrolment \leq 18 years.
- 3) Female of child-bearing potential must have a negative pregnancy test at the beginning of the trial, and then every 3 months. If sexually active, they must agree to use adequate contraception, throughout study participation, and must have no intention of conceiving during the course of the study. Post-pubertal males must have no plans to father a child during the study and agree to use adequate birth control methods if sexually active.

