- 4) Ability to comply with the entire study procedures, ability to communicate meaningfully with the investigational staff, competence to give written informed consent; to be applied to the parents and/or patients, as appropriate
- 5) Duly executed, written, informed consent obtained from the parents/patient.

Exclusion Criteria. Any of the following will exclude a patient from this trial:

- 1) Neutrophil count $<1,500/\text{mm}^3$ and/or platelet count $<50,000/\text{mm}^3$
- 2) Demonstration of cutaneous or gastrointestinal ulceration of JDM related pulmonary disease or cardiomyopathy at the time of diagnosis.
- 3) History of poor compliance.
- 4) Evidence of current use of alcohol or illicit drugs abuse.
- 5) Live vaccines not allowed during the entire duration of the trial.

Dropout Criteria. Patients will be considered "treatment failures", and dropped from the trial but included in efficacy analysis, if any of the following will occur during the active period of the trial.

- 1) Non compliance with study medication administration
- 2) Enrolment in other therapeutic trials.

Feasibility study for sample size calculation: from the analysis of the 295 patients with JDM enrolled in a previous PRINTO study (EU contract QLG1-CT-2000-00514) (4) it can be inferred that the network can enrol in a 2 years frame up to 190 children with less than 12 months disease duration (of whom 140 with disease duration less than 6 months).

Sample size calculation for superiority trial. We used the PRINTO JDM definition of improvement (see previous section "definition for primary outcome") (4) for sample size calculation for superiority trials.

We carried out sample size calculations based on the information obtained from a study on JDM patients conducted by PRINTO with a previous grant (contract EU contract QLG1-CT-2000-00514). In the study a total of 284 JDM patients with a mean age at onset of 7.6 years (Standard Deviation [SD] 3.9) the observed improvement rate was 83% after 6 months of therapy with PDN combined with MTX or CSA. We estimated that the group treated only with PDN will have a response rate equal to 53%.

Using the sample size calculation for superiority trials and considering a drop out rate of 15%, a sample size of **40 patients in each group for a total of 120 patients**, will be required. The trial will have 0.8 power for comparisons of the combined treatment arms (PDN+MTX or PDN+CSA) to the reference treatment arm (PDN alone).

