If enrolment will proceed faster than expected we will collect 54 patients per arm for a total of 162 patients, 0.9 power, 0.05 type I error.

Below is a table with different sample size calculations, using different levels of power.

| Variable | PDN treatment | delta | alfa | Power | N per arm | Drop-out N/(1-0.15) |
|-----------------|---------------|-------|------|-------|-----------|---------------------|
| PRINTO JDM def. | 53 | 30% | 0.05 | 0.8 | 34 | 40 |
| PRINTO JDM def. | 53 | 30% | 0.05 | 0.9 | 46 | 54 |

Procedures in the Case of Adverse Events. In the event of clinical or laboratory AE, the attending physician should make the clinical decision as to which medication is most likely the cause of the AE. The suspected medication (experimental or allowed) should be stopped or dosage reduced for 1 or 2 weeks. If the AE disappears or significantly ameliorates then the medication will be reinstated. If the AE does not disappear the physician will either drop the patient from the trial, or repeat the procedure with one of the remaining drugs. The drug that was initially discontinued (experimental or allowed) may be reinstated (as deemed appropriate by the attending physician), once it has been shown not to be the cause of the AE.

Withdrawal From the Trial. The attending physician will determine, clinically, if a patient should be removed from the trial, stating the reason for the early termination on the appropriate

form. The attending physician will be also responsible for reporting all clinically significant drug related AE. These will be graded on a three-point scale (mild, moderate, severe), and the relationship with the study medication will be assessed as definite, probable, possible, unlikely or no association as defined in the AE form. Any unexpected, life threatening or fatal AE will be reported by telephone within 12 hours after the AE, to the coordinating centre, followed by detailed medical description of the AE, along with copies of all pertinent medical records.

Clinical and laboratory evaluation. Monthly up to 6 months, then every 3 months up to 24 months, then every 6 months up to month 60.

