Statistical Analysis. The values at the final visit for the core set variables will be compared to the baseline values. Furthermore, patients will be dichotomously classified as "responders" or "non-responders" according to the validated JDM definition of improvement. Descriptive statistics will be used for reporting adverse events. For proportional data the chi-square test, or where appropriate the Fisher's exact test, will be applied. For continuous variables the t-test procedure or the ANOVA, will be applied as appropriate. Non parametric ANOVA will be applied in case of ordinal data or not-normally distributed variables; the Dunnett test will be used as a posterior test. Treatment effect size will be calculated by dividing the difference between the baseline and the final visit value, by the standard deviation of the first visit value. Survival analysis with censored data will be used in order to evaluate time to remission and time to flare. Survival curves will be drawn with the Kaplan-Meyer method and compared with the log rank test. For multiple hypothesis testing, alpha level is set at 0.01. Emphasis will be placed on the intention-to-treat approach rather than on analysis of only the completers of the trial. All analysis will be done in a blinded manner.

Table: Time Oriented Table and duration time for each task

| Task No | Months | 1 | 2 | 3 | 4 | 5 | 6 | 7 | 8 | 9 | 10 | 11 | 12 | 13 | 14 | 15 | 16 | 17 | 18 | 19 | 20 |
|---------|--|---|---|---|---|---|---|---|---|---|----|----|----|----|----|----|----|----|----|----|----|
| 1 | Personnel selection and training | | | | | | | | | | | | | | | | | | | | |
| 1 | Translation of material | | | | | | | | | | | | | | | | | | | | |
| 1 | Data base and case report form development | | | | | | | | | | | | | | | | | | | | |
| 1 | Submission to ethics committee | | | | | | | | | | | | | | | | | | | | |
| 2 | Trials enrolment | | | | | | | | | | | | | | | | | | | | |
| 3 | Interim analysis | | | | | | | | | | | | | | | | | | | | |

| Task No | Months | 21 | 22 | 23 | 24 | 25 | 26 | 27 | 28 | 29 | 30 | 31 | 32 | 33 | 34 | 35 | 36 | 37 | 38 | 39 | 40 |
|---------|---------------------------|----|----|----|----|----|----|----|----|----|----|----|----|----|----|----|----|----|----|----|----|
| 2 | Trials enrolment | | | | | | | | | | | | | | | | | | | | |
| 2 | Trial long term follow-up | | | | | | | | | | | | | | | | | | | | |
| 3 | Interim analysis | | | | | | | | | | | | | | | | | | | | |

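### Time to remission is a fixed target tested by a log-rank test that ignores baseline severity; a pre-specified adjusted Cox model is a cheap improvement

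*Protocol*

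**What the plan says.** - Protocol, Primary Outcome Measures after 24 months of treatment: the first of two outcomes is "time to clinical remission on medication defined as normal muscle strength and physician global assessment of disease activity equal to 0". The definition makes no reference to the child's own baseline.
- Protocol, Primary Outcome Measures after 6 months of treatment: response is relative to baseline, requiring "at least 20% improvement in at least 3 core set variables". Physician global and CMAS are both in the core set.
- Protocol, Statistical Analysis: "Survival analysis with censored data will be used in order to evaluate time to remission and time to flare". The comparison is then fixed: "Survival curves will be drawn with the Kaplan-Meyer method and compared with the log rank test". No covariate, stratum or regression model is named. The same section compares core set values at the final visit with baseline, so the baseline values are collected.
- Protocol, Dose Regimen: methylprednisolone pulses are "followed by randomisation into one of these 3 groups". No balancing factor is named.
- Protocol, Sample size calculation for superiority trial: "40 patients in each group for a total of 120 patients", computed on the 6-month response rate. If enrolment is fast, "we will collect 54 patients per arm for a total of 162 patients, 0.9 power, 0.05 type I error". No event count or power is given for time to remission.
- Entry sets no core set threshold. The Exclusion Criteria remove some severe organ involvement, which narrows the spread of severity without removing it.

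**The concern.** A percentage-change endpoint takes some account of where each child starts. A fixed endpoint does not: a child who enters with a low physician global and near-normal strength has less far to go than one who enters very weak. If severity at entry is prognostic in this way, a test that ignores it has two costs. It gives up power that the baseline data would supply, and its result moves with whatever severity difference randomisation happens to produce between small arms. Both matter more here because the outcome is primary, the disease is rare, and the sample size was not derived for this endpoint.

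**Working it through.** **1. The plan's own figure.** Inputs from the sample size section: 53% v 83%, alpha 0.05, dropout 15%. Two proportions, unpooled variance, two-sided:

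n = (1.960 + 0.842)² × (0.53×0.47 + 0.83×0.17) / 0.30² = 7.849 × 0.3902 / 0.09 = 34.03

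This is the stated 34, and 34/0.85 = 40. At power 0.9, n = 45.56, so 46, and 46/0.85 = 54.1 (stated 54). The figures reproduce, but only for the 6-month response.

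**2. What 40 per arm gives for time to remission.** Schoenfeld, one combination arm against PDN: detectable HR = exp(2 × (1.960 + 0.842)/√D), with D events in 80 children. The share remitting is assumed.

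| Share remitting | D | HR at 80% power, alpha 0.05 | alpha 0.01 |
|---|---|---|---|
| 40% | 32 | 2.69 | 3.35 |
| 60% | 48 | 2.25 | 2.68 |
| 80% | 64 | 2.01 | 2.35 |

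The 0.01 column uses the level that the Statistical Analysis section sets for multiple testing.

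**3. Chance imbalance.** The difference in a baseline mean between two arms of 40 has SD √(2/40) = 0.224 SD units, so its 95% range is ±0.44. P(|difference| > 0.3 SD) = 2 × (1 − Φ(0.3/0.224)) = 0.18. At 54 per arm it is 0.12.

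**4. Power with and without adjustment.** The documents give no remission rate, treatment hazard ratio or prognostic strength, so all three are assumed. Two settings were simulated, each one combination arm against PDN, 40 per arm, two-sided 0.05:

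- Setting A: PDN remission 50% at 24 months, treatment HR 2.0, one severity covariate, the protocol's visit grid, 15% dropout, 2,000 trials per row.
- Setting B: PDN remission about 40%, treatment HR 1.9. Gains are given for one covariate and, in separate runs with 15% dropout, for two covariates as in the fix.

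| Severity HR per SD | A: log-rank | A: log-rank stratified at median | A: adjusted Cox | A: Cox gain | B: gain, one covariate | B: gain, two covariates |
|---|---|---|---|---|---|---|
| 1.0 | 64.5% | 63.9% | 63.8% | -0.7 | not run | about -1 |
| 0.7 | 60.7% | 61.2% | 62.5% | 1.8 | 3 | 2 |
| 0.6 | 58.1% | 61.3% | 63.6% | 5.5 | 7 | 5 |
| 0.5 | 50.4% | 58.5% | 63.7% | 13.3 | 10 | 8 |

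(In A the log hazard ratios per SD were 0, 0.35, 0.5 and 0.7; exp(−0.35) = 0.70, exp(−0.5) = 0.61, exp(−0.7) = 0.50.) Simulation error in A is about ±1 point. At severity HR 0.6 in setting A, changing one input at a time:

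- PDN remission 30%: 43.1% v 44.7%
- PDN remission 70%: 66.0% v 73.9%
- 54 per arm: 68.3% v 76.8%
- Alpha 0.01: 32.7% v 37.4%

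**5. Sensitivity to the draw.** Setting A, severity HR 0.6. When the combination arm is sicker by more than 0.3 SD, log-rank power is 33%; when it is milder by that much, 81%. Adjusted Cox gives 60% in both (error about ±4 points). The unadjusted log HR moves by about 0.49 per SD of imbalance, so 0.44 SD multiplies the HR by exp(0.49 × 0.44) = 1.24.

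**6. Type I error.** With no treatment effect, the log-rank rejected overall in 4.7 to 5.1% of trials in setting A over the four severity hazard ratios tabulated, and in 3.6 to 4.6% in the two-covariate runs of setting B. Among only the roughly 18% of trials with imbalance above 0.3 SD, it rejected in 6.0%, 8.6% and 9.0% at severity HR 0.7, 0.6 and 0.5 (40% PDN remission, 20,000 trials per setting). Setting A gave 6.6%, 7.8% and 13.1%, each from only about 0.18 × 2,000 = 360 trials.

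**The case against.** The strongest reply is that nothing in the protocol is wrong. Under randomisation the log-rank test is valid for any time-to-event endpoint, fixed target or not, and covariates are often left to an analysis plan that is not shown here. The first part stands, and it limits the point to efficiency. The second stands only in part: the protocol does name the test for a primary outcome, so the choice can be judged as stated, although an analysis plan might already add adjustment.

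A reader might infer from the 6 to 9% rejection rate in imbalanced trials that alpha is inflated. It is not. In a comparable run, the other 82% or so of trials rejected in 3.6 to 4.0%, and the overall rate was 4.3 to 4.4%.

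The shift from a typical imbalance is also modest against ordinary sampling error. At severity HR 0.6, 0.3 SD moves the log HR by 0.3 × 0.51 = 0.15. With about 41 events (40 × 0.40 + 40 × 0.62), the standard error is about 2/√41 = 0.31, so the shift is half a standard error and the usual confidence interval already allows for it.

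It also stands that the gain rests on assumed prognostic strength and can be nil. Finally, the protocol's silence on stratified randomisation does not show that no factor was balanced.

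**Conclusion.** This is a cheap improvement, not an error. The plan names a valid but less efficient test for a primary outcome whose fixed definition probably makes severity at entry matter. Over assumed severity hazard ratios of 1.0 to 0.5 per SD, adjustment changes power by about -1 to +13 points, and by about 2 to 7 points at 0.7 to 0.6. It also makes the result less dependent on an imbalance that exceeds 0.3 SD in 18% of pairs of arms of this size. That severity delays remission is inferred from the definition; the documents give no figure for it.

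Two stronger readings are not supported. The unadjusted log-rank is neither biased nor anti-conservative overall. Nor does adjustment rescue the endpoint: in setting A, adjusted power stays near 63% at alpha 0.05 even with an assumed treatment HR of 2.0. The absence of a sample size for remission is a separate matter.

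**What to change.** In the Statistical Analysis section, make the primary test of time to remission a Cox model with treatment, baseline physician global and baseline CMAS, both as continuous covariates. Define baseline as the last value recorded before randomisation; this needs saying because methylprednisolone pulses precede randomisation. Keep the Kaplan-Meier curves and the unadjusted log-rank as supportive. A log-rank stratified at the median is not an equal substitute: in setting A it gained 0.5, 3.2 and 8.1 points at severity HR 0.7, 0.6 and 0.5, against 1.8, 5.5 and 13.3 for the Cox model.

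The cost is small, since both scores are already in the core set. It comes to two extra model terms, a proportional-hazards check, a hazard ratio that is conditional on severity rather than marginal, and about 1 point of power if severity turns out not to be prognostic. Fixing the covariates in advance also avoids a dispute over post hoc adjustment should the arms differ at entry.

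### The trial is sized at alpha 0.05 but the analysis section sets 0.01 for multiple testing; if 0.01 governs the combination-versus-prednisone comparisons, power is about 0.53-0.59 each, not 0.8

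*Protocol*

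**What the plan says.** The overall hypothesis covers two combinations: "combination therapy of corticosteroids and either MTX or CsA will prove more effective and safe than corticosteroids alone".

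The section on sample size for a superiority trial assumes 83% response at 6 months on a combination and 53% on PDN alone. It concludes: "The trial will have 0.8 power for comparisons of the combined treatment arms (PDN+MTX or PDN+CSA) to the reference treatment arm (PDN alone". Its table uses alpha 0.05 in both rows: 34 per arm (40 with 15% drop-out) for 0.8 power, and 46 (54) for 0.9. The text on faster enrolment repeats this: "54 patients per arm for a total of 162 patients, 0.9 power, 0.05 type I error".

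The Statistical Analysis section assigns chi-square or Fisher's exact test to proportions, t-test or ANOVA to continuous data, non-parametric ANOVA to ordinal or non-normal data, and the log-rank test to remission and flare. Within the sentence on non-parametric ANOVA it adds that "the Dunnett test will be used as a posterior test". After the survival methods comes the general rule: "For multiple hypothesis testing, alpha level is set at 0.01". It names no outcome, comparison or family.

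There are also further primary outcomes at 24 months, time to remission and time to flare ("Primary Outcome Measures after 24 months of treatment: a) time to clinical remission on medication").

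**The concern.** Two active arms, each tested against one control, are multiple tests in the ordinary sense, so the 0.01 rule can be read as covering exactly the comparisons that were sized at 0.05. The Dunnett sentence does not settle this, because it is attached to continuous or ordinal data while responder proportions go to chi-square or Fisher.

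The success threshold for the sized endpoint is therefore undefined. A p-value between 0.01 and 0.05 is a success by the sample size section and may be a failure by the analysis section, and the choice could be made after the data are seen.

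**Working it through.** **Inputs.** From the sample size section: p1 = 0.53, p2 = 0.83, d = 0.30; alpha 0.05; power 0.8 or 0.9; drop-out 15%, applied as N/(1-0.15). From Statistical Analysis: alpha 0.01; chi-square or Fisher for proportions. Sidedness is not stated; two-sided is inferred because it reproduces the protocol's N best.

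**1. Reproduce the stated N.** Unpooled normal formula, n = (z_a + z_b)² × [p1q1 + p2q2] / d², with p1q1 + p2q2 = 0.2491 + 0.1411 = 0.3902:
- alpha 0.05, power 0.8: (1.960 + 0.842)² × 0.3902 / 0.09 = 34.03. Stated 34; 34/0.85 = 40.
- alpha 0.05, power 0.9: (1.960 + 1.282)² × 0.3902 / 0.09 = 45.56. Stated 46; 46/0.85 = 54.1, stated 54.

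The sizing arithmetic is sound at two-sided 0.05 for one 1:1 comparison, with no allowance for the second.

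**2. Power at 0.01 with the same N.** With 34 per arm:
- Unpooled: the standard error is √(0.3902/34) = 0.1071 and d/SE = 2.800. At 0.05, Φ(2.800 - 1.960) = 0.800. At 0.01, Φ(2.800 - 2.576) = 0.589.
- Pooled null variance (mean rate 0.68, 2 × 0.68 × 0.32 = 0.4352, standard error √(0.4352/34) = 0.1131): at 0.01, Φ((0.30 - 2.576 × 0.1131)/0.1071) = Φ(0.080) = 0.532.

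| Analysed per arm | alpha | Pooled | Exact chi-square | Unpooled (protocol's formula) | Stated |
|---|---|---|---|---|---|
| 34 | 0.05 | 0.767 | 0.787 | 0.800 | 0.8 |
| 34 | 0.01 | 0.532 | 0.550 | 0.589 | 0.8 |
| 40 | 0.01 | 0.624 | 0.643 | 0.678 | 0.8 |
| 46 | 0.05 | 0.882 | 0.887 | 0.903 | 0.9 |
| 46 | 0.01 | 0.704 | 0.724 | 0.752 | 0.9 |

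The row for 40 assumes that everyone randomised is analysed and that drop-outs do not dilute the effect. Fisher's exact test at 0.01 with 34 per arm has power 0.45.

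**3. At least one success.** Simulating both combinations at 83% against a shared control at 53%, the chance that at least one reaches 0.01 is 0.71 (34), 0.80 (40) and 0.86 (46).

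**4. Error if 0.05 applies to each.** With equal arms and a shared control the two statistics have correlation 0.5. The chance of at least one false positive is 0.091 at 0.05 each and 0.019 at 0.01 each. If 0.05 applies to response and 0.01 to four pairwise remission and flare tests, treating outcomes as independent, the total is 1 - (1 - 0.091) × 0.99⁴ = 0.127.

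**5. How often the two thresholds disagree.** Under 83% v 53%, the chi-square p-value of one comparison falls between 0.01 and 0.05 with probability 0.237 (34), 0.192 (40) and 0.163 (46). For example, against 18/34 responders on PDN, 26/34 gives p = 0.042 and 27/34 gives p = 0.021; only from 28/34 (p = 0.0095) is 0.01 met. By Fisher's test the same thresholds need 27/34 and 29/34.

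**6. N that would hold the stated power at 0.01.** The protocol's formula gives 50.6 and 64.5, so 51 and 65 evaluable; 51/0.85 = 60 and 65/0.85 = 76.5, so 77 enrolled per arm. The pooled formula gives about 56 and 70 evaluable (66 and 83 enrolled).

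**The case against.** The strongest reply is that the specific statement governs the general one. The protocol ties 0.05 to the sized outcome three times, once in text and twice in the table, whereas the 0.01 sentence names no outcome and follows a list of methods serving many endpoints. On that reading 0.01 is for everything else, and the stated power stands. This reading is possible, but the protocol does not state it, and it leaves the two response tests unadjusted at about 9%. Whether two different drugs against one control need joint adjustment is debated; the protocol should then say that it chose not to adjust.

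A second reply is that the multiplicity family is normally defined in an analysis plan, which was not available here. That would answer a complaint of omission. Here the protocol itself fixes two alphas, and a power figure that holds under only one.

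Other points soften the size without removing it:
- **Analysed number.** Intention-to-treat is emphasised and dropped patients stay in the efficacy analysis as failures. With 40 analysed and no dilution, power at 0.01 is 0.62-0.68.
- **Sidedness.** A one-sided 0.01 test with 34 per arm gives 0.63-0.68.
- **Pooled arms.** If both combinations were merged against PDN (68 v 34), power at 0.01 would be about 0.70-0.73, but the N per arm comes from a 1:1 comparison.
- **Mixed-reading total.** The 13% assumes pairwise log-rank tests; the protocol may intend one three-arm test per outcome.

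**Conclusion.** The concern holds. The sample size calculation is correct at 0.05; the defect is two unreconciled alpha levels for the comparisons on which the trial was sized. That contradiction is unconditional, while its consequence depends on the reading:
- If 0.01 governs, power per comparison is 0.53-0.59 against 0.8, and 0.70-0.75 against 0.9.
- If 0.05 governs each comparison, power is 0.77-0.80 and 0.88-0.90, without family-wise control on response.

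These figures rest on the protocol's 53% and 83%, two-sided tests, and 34 or 46 evaluable per arm. No alternative examined above brings power at 0.01 up to the stated 0.8 for the smaller design at its 34 evaluable per arm. Because the success threshold is at stake, it has to be settled before unblinding.

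**What to change.** State which alpha governs the two 6-month response comparisons and whether it is two-sided, and make the power statement match. Either option works:

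1. **Keep 0.01 for both comparisons.** Restate power per comparison as about 0.55-0.59 with 34 evaluable per arm and 0.72-0.75 with 46 (exact chi-square to the protocol's formula).
2. **Control response at a family-wise 0.05.** For example, run the three-arm chi-square at 0.05 and, only if it is significant, the pairwise tests at 0.05. Simulated family-wise error under the null is 0.048-0.055. Restate power per comparison as about 0.75 (34), 0.81 (40) and 0.87 (46) if both combinations work, or 0.72, 0.79 and 0.86 if only one does. Keep 0.01 for the other outcomes and say so.

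The cost is a change of wording in two sections and a less favourable power figure; no extra patients are needed if that is accepted. Holding 0.8 or 0.9 at 0.01 would take 60 or 77 enrolled per arm by the protocol's formula (66 or 83 by the pooled one), against 40 or 54 now.
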